### **Pregnancy**

Elective bunion surgery will not be performed if the patient is pregnant or planning on becoming pregnant during this study. It is standard practice to obtain urine testing in all women of child bearing potential prior to elective surgery to ensure she is not pregnant. Furthermore, if the subject is a woman capable of becoming pregnant, she must agree to use adequate birth control. For the purpose of this study, use of adequate birth control includes one of the following:

1. oral hormonal contraceptives;
2. implanted hormonal contraceptives (intramuscular progesterone injections);
3. diaphragm with spermicide;
4. condoms;
5. Intra-uterine device;
6. abstinence.

In the event a patient believes she may have become pregnant while participating in this study, she must inform the study investigator immediately and take a pregnancy test. If it is determined that she is pregnant, she must withdraw from the study immediately.

If the subject is a man capable of fathering children, he must use adequate contraception while participating in this study. For the purposes of this study, adequate birth control means;

1. use of a condom or
2. his partner must use an approved method of birth control as listed above or his partner has experienced menopause or has had a hysterectomy or
3. abstinence

#### **B4. POSSIBLE BENEFITS**

No benefit is guaranteed to the patient for the participation in this study.

The primary objectives of the Kalish procedure are to reduce pain and improve function. All surgical procedures, even if they are elective out-patient surgeries, are associated with post-operative pain. As care providers, surgeons seek to achieve these surgical objectives while minimizing the pain that their patients experience. COX-2 inhibitors were considered to be an alternative to traditional NSAIDs but their use have suffered substantial drop off given concerns over potentially life-threatening adverse events. Ketorolac is a nonselective NSAID, inexpensive and widely available. Prior literature demonstrates that NSAID use in the post-operative period may reduce overall pain experienced and the frequency of opioid use. This represents a possible benefit to patients. Many surgeons already use ketorolac as described in this protocol, while others have concerns about delay in bone healing. The proposed study would provide evidence that has the potential to impact the standard of care throughout the United States in podiatric and orthopedic communities.

For the medical community as a whole, regardless of the outcome, this study and subsequent publications will represent the first randomized control trial on this topic. The study design will test the hypothesis such that the results will provide strong evidence that will advance either the supportive or detracting arguments.

#### **B5. POSSIBLE RISKS AND ANALYSIS OF RISK/BENEFIT RATIO**

There is a potential risk that patients randomized to the ketorolac group may experience adverse events. Our inclusion/exclusion criteria were carefully designed to prevent enrollment of study subjects at risk for developing adverse events related to ketorolac. Only patients between the ages of 18 – 65, with an ASA less than four will be enrolled. In addition, patients with coagulation disorders, history of gastrointestinal bleeding or ulcer, renal failure (as defined by creatinine >1.5 ml/dL, utilizing other studies as reference), or blood urea nitrogen levels >22 mg/dL will be excluded from the study (please refer to inclusion/exclusion criteria for full details). This will eliminate subjects at the greatest risk for developing ketorolac related adverse events. Finally, we are utilizing a low recommended dose of ketorolac with a total duration of five days to also minimize potential side effects. If however, a patient does experience an adverse event believed to be related to ketorolac, they will be instructed to immediately contact his/her surgeon and discontinue the medication. All adverse events will be reported, following all of our institution's IRB guidelines and protocols.

There will be a mechanism in place in the event there is an emergency to unblind any necessary individuals. All patients will be given the on-call podiatry pager number and instructed to utilize this number if they experience any adverse events or concerns. One of the podiatry investigators will be on-call and available to study patients at all times. The surgeon investigator will have the capability of determining whether or not the patient should discontinue the study and can unblind anyone he/she deems necessary by contacting research pharmacy should an emergency or adverse event occur.

Most of the post-operative course is considered standard of care. It will be explained in advance to patients that they will be asked to fill out a study diary, be contacted approximately two days following the surgery, and asked to remember to bring in the diary and all pain medication during his/her first post-operative visit. The duration of the telephone call two days post-operatively is estimated to take approximately 20 minutes based upon adding up the reported time of the individual questionnaires in previous studies (54,55). Although this will consume a portion of the patient's time, the patient will be made aware of the telephone call and duration in advance and has the opportunity to decline participating in this study. This also gives the patient the opportunity to report any problems he/she may be experiencing post-operatively.

There will also be procedures in place for protecting patient confidentiality. All data (CRFs, source documents, patient's questionnaire, patient diaries) will be stored in locked cabinets at [name] office. Only study personal will have access to these cabinets. Clinic notes and radiographs will be entered into the internal BIDMC online medical record (OMR) within the BIDMC secure server, behind the BIDMC firewall. Only personnel approved by our institution's IRB will be allowed to access this information. Research personnel in our group who have a need to access patient information have been trained to be highly sensitive to patients and their protected health information. In addition, all patient/subject protected health information is stripped from radiographic images and other data when they are moved to other computers for data processing.

The benefits of this treatment protocol to the individual and to the population at large clearly outweigh the risks to both groups.

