### B3. DESCRIPTION OF RESEARCH PROTOCOL

#### A. Study Design – Overview, Methods, Procedures

##### A.1. Overview

This will be a prospective randomized double-blinded clinical trial that will accept all eligible consecutive patients undergoing elective Kalish bunionectomies (Figure 1). Patients will be randomized into either receiving ketorolac (30 mg IV dose intra-operatively followed by 10 mg orally every 8 hours for five days) plus standard of care or placebo (one pill every 8 hours for five days) plus standard of care. Patients will be assessed for pain via a validated pain questionnaire and for nonunion via a radiographic scoring system that has both high inter- and intra-observer reliability by a blinded assessor (41).

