## **C. Subject Selection**

### **Assembly of subjects**

All patients undergoing a first metatarsal Kalish osteotomy for bunion correction who meet study inclusion and exclusion criteria will be invited to participate in this study.

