### **Inclusion Criteria:**

- Hallux abductus with bunion deformity
- Adult patients as defined by  $\geq 18$  years old and  $\leq 80$  years old
- Subject has adequate perfusion, verified by the surgeon, which is defined by palpable pedal pulses
- Subject has voluntarily signed and dated an informed consent form, approved by an Institutional Review Board, and provided HIPAA (or other applicable privacy regulation) authorization prior to any participation in the study
- Subject agrees not to take any new medications, dietary supplements, or alternative therapies during the study period (approximately 12 weeks)
- Subject is interested in participating in the study and willing to comply with the study protocol
- Patient has pain related to a bunion deformity but pain-free metatarsalphalangeal joint (MTPJ) range of motion that is not functionally adapted
- Adequate bone density to withstand a Kalish bunionectomy procedure
- No frontal plane hallux deformity
- Minimal abnormality of the PASA

- Normal to minimally malaligned sagittal plane position of the first metatarsal
- Failure of conservative treatment
- General Pre-operative Radiographic Angle Criteria†
  - 10-15 IMA in rectus feet\*
  - 20-25 TAA in adducted feet\*
  - 15-20^0 IMA in rectus feet if wide metatarsal head width
  - 25-30^0 TAA in adducted feet if wide metatarsal head width

*IMA=intermetatarsal angle; TAA=total adductus angle*  
\*If the pre-operative IMA is <15, only the IMA will be used pre-operatively. For IMA ≥15, the total adductus angle will be used  
†These are general guidelines and the width of the metatarsal as well as the presence of positional, structural, or combined first ray deformity may also influence procedure selection (51-52).

Exclusion Criteria:

- Patients with a contraindication for ketorolac will be excluded from the study. This includes patients with:
  - a history of an allergic-type reaction in response to exposure to aspirin, phenylacetic acid derivatives, or other NSAIDs
  - hypersensitivity to ketorolac tromethamine, or to any product component
  - any known bleeding risk or bleeding disorder, suspected or confirmed
  - history of or active cerebrovascular bleeding, suspected or confirmed
  - concomitant aspirin or NSAID use where the patient may not be advised to discontinue the medication during the study
  - concomitant pentoxifylline use
  - concomitant probenecid use

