  - coronary artery bypass graft (CABG) surgery within one year of the procedure
  - any history of gastrointestinal bleeding/perforation, gastrointestinal ulcer, severe peptic ulcer disease, or severe inflammatory bowel disease
  - hemorrhagic diathesis, suspected or confirmed
  - incomplete intraoperative hemostasis
  - pre-operative serum creatinine > 1.5 ml/dL or blood urea nitrogen level > 22 mg/dL
  - any history of renal impairment or risk of renal failure due to volume depletion
- Patients with a known allergy, contraindication and/or intolerance for oxycodone 5mg – acetaminophen 325 mg will be excluded from the study.
- Patients with a known allergy, contraindication, and/or intolerance for the local anesthetic (bupivacaine) or any of the standardized intra-operative opioids and anti-emetics administered by the anesthesiologist
- Patients with a history of fibromyalgia or opioid abuse
- History of chronic regional pain syndrome or diagnosis of any chronic pain syndrome, patients requiring routine methadone or other opioids
- Neuropathy or radiculopathy
- Subject has alcohol or substance abuse, dementia, brain metastases, or other cognitive disorders that may interfere with pain assessment and the post-operative course outlined by the surgeon

- Patients with a contraindication for elective surgery will be excluded and includes:
  - American Society of Anesthesiologists (ASA) Physical Status class four or higher
  - women who are pregnant, planning on becoming pregnant, or breast feeding
  - presence of active local or systemic infection
  - subject has a myocardial infarction in the last twelve months
  
- Patients who are not candidates for a Kalish bunionectomy due to the preoperative deformity as well as other study exclusions are:
  - Absent pedal pulses or  $ABI \leq 0.9$  and  $\geq 1.2$
  - Concomitant midfoot and rearfoot procedures
  - Moderate to high abnormal PASA angles
  - Significant sagittal plane first metatarsal deformity
  - Moderate to severe osteoporosis as evaluated by preoperative radiographs and/or bone mineral density tests
  - Revision cases
  - History of previous infections, radiation treatment, or current infection related to the surgical site
  - History of previous trauma of the first metatarsal or first ray
  - Subject has known immunosuppression (HIV, recent chemotherapy, organ transplant)

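### The inclusion criteria admit patients aged 18 to 80, but the risk/benefit section says enrolment is limited to ages 18 to 65

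*Combined protocol and SAP*

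**What the plan says.** The eligibility rule is in section B3.C (Subject Selection). The age item under Inclusion Criteria reads "Adult patients as defined by $\geq 18$ years old and $\leq 80$ years old". The Exclusion Criteria that follow contain no age item.

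Section B5 (Possible Risks and Analysis of Risk/Benefit Ratio) gives a different range. It first explains the purpose of the criteria: "Our inclusion/exclusion criteria were carefully designed to prevent enrollment of study subjects at risk for developing adverse events related to ketorolac". The next sentence is "Only patients between the ages of 18 – 65, with an ASA less than four will be enrolled". B5 then lists coagulation, gastrointestinal and renal exclusions, refers the reader to the eligibility list ("please refer to inclusion/exclusion criteria for full details"), and concludes that those most prone to ketorolac-related events are thereby kept out.

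The sections that govern recruitment work from the eligibility list. The Overview (B3.A.1) says that the trial will "accept all eligible consecutive patients undergoing elective Kalish bunionectomies". Assembly of subjects (B3.C) says that patients "who meet study inclusion and exclusion criteria will be invited to participate in this study". The screening text in A.4.a and in B6 also has the surgeon check the medical record against the inclusion and exclusion criteria.

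**The concern.** A patient aged 66 to 80 is eligible under the inclusion criteria and ineligible under B5. Three things follow.

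- **Who is enrolled.** Screening follows the list and the trial takes consecutive eligible patients, so patients aged 66 to 80 would be invited although B5 says they will not be enrolled.
- **What was weighed.** B5 names the age range among the safeguards against ketorolac adverse events and goes on to conclude that the benefits outweigh the risks. That argument is written for a narrower population than the one the list admits.
- **What counts as a deviation.** The Missing Data section requires protocol deviations to be recorded and reported. From this text one cannot say whether enrolling a 70-year-old is a deviation.

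**Working it through.** No power, alpha or event calculation bears on this point. The check is a comparison of the two sections, followed by a search for anything that reconciles them.

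**Step 1: compare every numeric limit that B5 repeats with the eligibility list in B3.C.**

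| Criterion | Section B5 | Eligibility list (B3.C) | Agree? |
|---|---|---|---|
| Age | 18 to 65 | 18 to 80 | Lower bound yes, upper bound no |
| ASA class | below 4 | excluded if "American Society of Anesthesiologists (ASA) Physical Status class four or higher" | Yes |
| Serum creatinine | excluded if > 1.5 | excluded if > 1.5 | Yes |
| Blood urea nitrogen | excluded if > 22 | excluded if > 22 | Yes |

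The list's entry for the last two rows is "pre-operative serum creatinine > 1.5 ml/dL or blood urea nitrogen level > 22 mg/dL". Three of the four limits match and one does not. B5 is otherwise an accurate restatement, so a reader has no reason to treat its age range as a loose paraphrase.

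**Step 2: size of the disagreement.**

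- Upper bounds: 80 − 65 = 15 years.
- Single years of age admitted by the list: 80 − 18 + 1 = 63.
- Single years of age admitted by B5: 65 − 18 + 1 = 48.
- Ages in dispute (66 to 80): 63 − 48 = 15, and 15/63 = 23.8% of the admitted age span.

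The last figure is the width of the rule. It is not a share of patients. The recruitment section gives visit volumes but no ages, so no count of affected patients can be derived.

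**Step 3: look for reconciling text.** No exclusion criterion sets an upper age. No other age limit appears in the available text. Neither statement belongs to an amendment log or a summary of changes, and neither shows a redaction or an extraction fault at the age limit. No rule of precedence between sections is given.

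**Step 4: take each reading in turn.** If the list governs, B5 misdescribes the enrolled population and cites a safeguard that is not in force. If B5 governs, the inclusion criterion is wrong and screening as described would enrol patients who should be kept out. One of the two sections must change on either reading.

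**The case against.** The strongest reply is that the working rule can be identified. Screening and invitation are tied to the inclusion and exclusion criteria, while B5 is a narrative summary that describes those criteria and sends the reader back to them. On that view site staff have one rule, 18 to 80, and the error is confined to the summary. The consequence is also limited: the ASA, renal, bleeding and gastrointestinal exclusions still apply to patients aged 66 to 80, and neither the randomised comparison nor the sample size depends on the age limit. The point might therefore be rated as minor.

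Part of this stands. The practical consequence is limited, and the 24% width figure should carry no weight in judging seriousness. The screening form is not among the documents, so it cannot be said to carry a wrong range.

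The reply does not remove the conflict. The pointer in B5 offers fuller detail without saying that the list overrides the stated limit, and it sits in the following sentence, which concerns exclusions. The age sentence itself is categorical. And if the list does govern, the risk/benefit argument describes a population other than the one to be enrolled, which is a fault in its own right.

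**Conclusion.** The concern holds. Two current sections give upper age limits of 80 and 65, a gap of 15 years, and nothing in the available text reconciles them.

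The finding rests only on eligibility and on the consistency of the ethics review. It makes no claim about how risk varies with age, which the documents do not address, nor about how many patients fall in the disputed range. It does not affect the validity of the treatment comparison, the randomisation or the sample-size calculation. It should still be corrected as a matter of necessity, because an enrolment threshold stated in two ways cannot be applied consistently, and the risk/benefit assessment should cover the population that is actually admitted. The documents do not show which limit was intended.

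**What to change.** Reconcile the Inclusion Criteria and section B5 to a single age range, and have the risk/benefit text describe that same population. As a precaution, confirm that the screening form carries the same range. Notify the IRB. This should be done before anyone is enrolled under the conflicting text; the documents do not state enrolment status, so if enrolment has begun, the sponsor should also establish which limit has been applied.

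The direct cost is one corrected number, a check of the screening form and an IRB notice. There is a further cost on either choice. If the wider range is kept, B5 has to be reworded to cover ages 66 to 80. If the narrower range is kept, the eligible pool shrinks by an amount the documents do not allow to be sized. Visits, randomisation, the sample-size calculation and the analysis do not change. The choice of limit belongs to the sponsor and the investigators, and none is proposed here.

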## **B6. RECRUITMENT AND CONSENT PROCEDURES**

### **Recruitment**

Previous long-term large clinical trials, through several NIH grants, have been conducted at our center. We will have access to a dedicated clinical research room as well as experienced and qualified research assistants who have successfully participated in numerous clinical trials. In addition, our facility hosts a dedicated two-year podiatric reconstructive and research fellowship and a podiatric medicine and surgery-36 residency.

Patients will be recruited from a large tertiary care institution which has one major primary foot and ankle clinic with satellite podiatry offices scattered throughout a metropolitan area. The demographics of the satellite patients are similar to those seen at the primary center for elective cases including bunionectomies. There are over 12,900 annual visits at the primary clinic and over 10,000 annual visits at the satellite clinics.

Surgical cases at our institution were reviewed for volume over the past two years. Adequate numbers of surgical cases were identified in both financial years 2007 and 2008 with 6 participating surgeons. An additional two surgeons have joined the staff in 2009 and volume is expected to either remain stable or increase. All eight surgeons are either board certified or board eligible by the American Board of Podiatric Surgery in both Foot Surgery and Reconstructive Rearfoot and Ankle Surgery. All are well versed in the indications and technique associated with the Kalish bunionectomy procedure. Please note that the power calculation also takes into account the estimated differences between surgeons by cluster analysis. Final analysis will also assess for differences between surgeons and surgeon experience and control for this by regression analysis if necessary.

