#### **A.6. Randomization and Blinding**

Eligible patients will be randomized in the pre-operative holding area to either ketorolac or placebo by stratified permuted block randomization. Stratification will be by number of forefoot procedures (isolated Kalish bunionectomy versus Kalish bunionectomy plus additional forefoot procedures) and by unilateral versus bilateral (total of four possible strata: 1. Unilateral + Isolated Kalish Bunionectomy; 2. Unilateral + Kalish Bunionectomy with additional forefoot procedures; 3. Bilateral + Isolated Kalish Bunionectomy on one side; 3. Bilateral + Kalish Bunionectomy with any additional forefoot procedures. Any correlated cases will be accounted for in the analysis and are not common at this institution (but will be stratified in the event they do occur to help ensure balance between the study groups).

Study group allocation will be controlled by research pharmacy with sequentially numbered opaque sealed envelopes. This communication will occur entirely between the surgeon and research pharmacy. Allocation of ketorolac or placebo will be recorded on a "Randomization/Treatment" log that will be stored in a secure location with both opened and unopened randomization envelopes.

Access to this secure location will be controlled and locked. A coded master list will be kept in a locked and secured cabinet.

Patients, surgeons, anesthesiologists, and any assessors will be blinded. Only research pharmacy will not be blinded. Both ketorolac and placebo capsules and bottles and intra-venous preparations will appear exactly the same and will be prepared by research pharmacy. Assessors will be collecting data on post-operative pain and radiographic unions and will not be made aware of the patient's randomization results. In the event of an emergency or where the subject safety may be at risk, research pharmacy will unblind any necessary individuals to properly care for patients. In this event, the details of revealing the assigned study drug must be recorded in the subject's source documents.

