### **B. Statistical Considerations**

#### **a. Sample Size Justification:**

In performing the required sample size calculations, the authors assumed that potential cluster effects may be evident as a function of the individual surgeon. Because of this likelihood of cluster effects, we estimate the power of the study for change in post-operative pain that assumes an intra-class correlation (ICC) of at least 0.08 to inflate sample size estimates. This assumes 80% power to detect differences between groups with a 0.05 two-sided significance. Previous literature reports that in comparisons of opioid alone versus ketorolac with opioid the mean difference was observed to be 1.8 on the VAS (16). The widely accepted minimum clinically significant pain relief has been reported to be 1.3 (17). Detection of a 1.3 absolute difference in change in pain relief between groups requires 40 patients per group; detection of a 1.8 difference requires 20 patients per group consisting of eight and four (surgeons) respectively, assuming clusters of 10 subjects each. These calculations use an extremely high ICC which maximizes its accuracy. Because of the unknown ICC influence, a sensitivity analysis was performed assuming a non-contributory ICC of 0.08 which required a total sample size of 20 subjects per arm using the smallest clinically significant difference to detect.

Based on these calculations the largest sample required is 80 subjects. In order to preserve statistical power in the face of drop-outs and patient contact difficulties, the total sample size will be inflated by 10% such that the final projected sample size will be 88 subjects, or 44 per arm.

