#### *b. Secondary Outcomes*

The proportion of rescue narcotics will be compared between the ketorolac and placebo groups. Narcotics will be converted to standard morphine equivalents for statistical comparison.

On day two, the research fellow will also ask patient's his/her Global Evaluation of Study Medication by telephone. The patient will be asked, "How would you rate the study medication you received to delay pain". The choices will be on a four point scale: 1=poor; 2=fair; 3=good; 4=excellent.

Adverse events will be obtained from a standard form included in the patient's study diary. The proportion of adverse events will be compared between the ketorolac and placebo groups.

Time to regular shoe gear will be compared between the two groups. This information will be assessed during the post-operative visits and recorded within the secure BIDMC online medical record for each patient. Level of post-operative activity will also be evaluated with the help of the functional recovery index. This is a validated instrument for post-operative patients which includes three main domains: 1. Pain and social activity; 2. Lower limb activity; 3. General physical activity.

Summary statistics will be analyzed and reported. Continuous data will be analyzed with a 2-sided student's t-test if normally distributed or a Wilcoxon Rank Sum test if it cannot be justified through the Central Limit Theorem. From this data, confidence limits will be obtained and a 2-sided p value of  $\leq 0.05$  from the Fisher Exact Test will be considered statistically significant. If there are significant confounders identified, multivariate regression or stratification may be required and utilized if necessary. Binary data points will be compared by chi square analysis. From this, 95% confidence intervals will be obtained as well as a p-value from the Fisher Exact Test. A compliers-only analysis will also be secondarily performed if necessary, with the notion that this part of the study may have confounders and will not be part of the randomized comparison. Table 1 of the study will detail subject ages, gender, comorbidities, and other baseline study demographics.

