### **Other Variables of Interest and Their Measurements**

Because this is a randomized trial, confounders should be equally distributed between the two treatment groups. All variables will be analyzed to check if there are any differences between the two groups.

There will be many variables collected for this study. These variables include the pain score evaluations, ages, genders, patient related contact information, comorbidities, tobacco use, medications, allergies, BMIs, laboratory results, all anesthesia medications used, number of millimeters the capital fragment was transposed, fixation specifics for the bunionectomies, intra-operative complications, tourniquet time, attending of record, attending experience, pain control given in post-anesthesia holding area, pain medication taken post-operatively, pill counting and mechanisms to assess patient compliance post-operatively, timing of the telephone interview and last dose of post-operative pain medication, post-operative protocol deviations, and whether or not physical therapy was used. The study and analysis will take place and be stored at Beth Israel Deaconess Medical Center. Follow-up visits may also occur at Beth Israel Deaconess Medical Center satellite clinics for patient convenience.

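### The primary pain model is not fixed in advance: the stratification factors and baseline pain are never named as terms, and surgeon enters only if judged necessary

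*Combined protocol and SAP*

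**What the plan says.** **Randomisation.** Section B3, A.6 uses permuted blocks within four strata: "Stratification will be by number of forefoot procedures" (isolated or with additional forefoot procedures), crossed with unilateral or bilateral surgery. It adds that correlated cases will be handled in the analysis, without saying how, and that they are uncommon.

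**Primary analysis.** The Primary Outcome text under Data Analysis commits to regression for measured confounders. It names two, the timing of the telephone interview and the last dose of pain medication, as examples from an open list. Model building follows unspecified standard rules, and significance at 0.05 is read from the final model.

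**Baseline pain.** A.4.a records pain scores on the day of surgery. No analysis section uses them as a covariate.

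**Surgeon.** The Sample Size Justification "assumes an intra-class correlation (ICC) of at least 0.08 to inflate sample size estimates", because of clustering by surgeon. The Recruitment section (B6) then says: "Final analysis will also assess for differences between surgeons and surgeon experience and control for this by regression analysis if necessary".

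**Other variables.** Under Other Variables of Interest: "All variables will be analyzed to check if there are any differences between the two groups". For secondary outcomes: "If there are significant confounders identified, multivariate regression or stratification may be required and utilized if necessary". Deviations in surgical technique or post-operative care are also to be allowed for in the analysis (A.3, A.4.b), with no method given.

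**The concern.** Two things are at stake.

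1. **Precision.** Stratified randomisation balances the arms on the stratifying factors. If these predict pain, the treatment estimate varies less from trial to trial than an unadjusted standard error implies. The test is then conservative, and the gain from stratifying is lost. Baseline pain is a second possible source of precision that is already collected and not named.

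2. **Discretion.** With an open covariate list, no stated selection rule, no criterion for including surgeon and the p-value taken from the last model, several analyses of the same data would all comply with the plan. The reported result could depend on which was chosen after the data were seen.

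**Working it through.** **Inputs from the documents.** "This assumes 80% power to detect differences between groups with a 0.05 two-sided significance". "Detection of a 1.3 absolute difference in change in pain relief between groups requires 40 patients per group; detection of a 1.8 difference requires 20". Surgeon ICC 0.08, clusters of 10, eight surgeons, four strata. "The widely accepted minimum clinically significant pain relief has been reported to be 1.3 (17"), so the difference used below is 1.3.

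**Inputs the documents do not give.** The SD of the pain score, the variance explained by the strata, the block size and the share of patients in each stratum. These are assumptions below.

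**Step 1: the plan's own figure.** The 40 per arm cannot be reproduced, because no SD is stated. Solving for the SD, with 1.960 + 0.842 = 2.802:
- no clustering: 1.3 / (2.802 × √(2/40)) = 2.08
- design effect 1 + (10 − 1) × 0.08 = 1.72: 1.3 / (2.802 × √(2 × 1.72/40)) = 1.58

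The two stated sizes agree with each other: 40 × (1.3/1.8)² = 20.9, against 20. The steps below use SD 2.08, which gives 80% power unadjusted at 40 per arm.

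**Step 2: closed form for the strata.** Suppose the strata explain R² of the variance and are balanced exactly. The true standard error is then √(1 − R²) times the unadjusted one.
- Type I error of the unadjusted test: 2 × Φ(−1.96/√(1 − R²)). For R² = 0.20: 1.96/0.894 = 2.19, giving 2.8%.
- Power, unadjusted: Φ((2.802 − 1.960)/√(1 − R²)).
- Power, adjusted: Φ(2.802/√(1 − R²) − 1.960).

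| R² | Type I error, unadjusted | Power, unadjusted | Power, adjusted |
|---|---|---|---|
| 0 | 5.0% | 80.0% | 80.0% |
| 0.05 | 4.4% | 80.6% | 82.0% |
| 0.10 | 3.9% | 81.3% | 84.0% |
| 0.20 | 2.8% | 82.7% | 87.9% |

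Comparing the adjusted column with a flat 80% would overstate the gain, because the balance from stratification already helps the unadjusted test a little.

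**Step 3: simulation.** 80 patients, 8 surgeons, ICC 0.08, blocks of 4, stratum shares of 50, 35, 8 and 7%, 4,000 runs per scenario. The Monte Carlo standard error is √(0.05 × 0.95/4000) = 0.3 points for type I error and √(0.8 × 0.2/4000) = 0.6 points for power.

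| Strata R² | Type I: unadjusted | Type I: strata in model | Type I: surgeon added only if its F-test has p ≤ 0.05 | Type I: smallest p of four models | Power: unadjusted | Power: strata | Power: strata + surgeon (7 fixed effects) |
|---|---|---|---|---|---|---|---|
| 0 | 5.0% | 5.0% | 5.3% | 7.2% | 79.2% | 78.9% | 77.3% |
| 0.05 | 4.3% | 4.6% | 4.6% | 6.7% | 78.5% | 80.2% | 79.6% |
| 0.10 | 4.0% | 5.1% | 4.4% | 7.6% | 79.0% | 81.9% | 81.3% |
| 0.20 | 2.8% | 4.6% | 2.9% | 6.4% | 81.7% | 87.0% | 86.5% |

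The four models are: no covariates, strata, surgeon, and both. The power gains from the strata are −0.3, 1.7, 2.9 and 5.3 points, in line with Step 2.

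**The case against.** The best defence is that the plan does more than it may seem to. Regression for the primary outcome is a commitment, with two covariates named. A reader might infer from the Recruitment and Secondary Outcomes wording that all adjustment waits on the data; for the primary outcome the text does not support that. The purely conditional sentence belongs to the secondary outcomes. Saying that the strata are ignored would also go too far: correlated cases are to be handled, and stratification is allowed as an option. What can be said is that the factors are not named as model terms.

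A reader might also infer that the between-group checks decide which covariates enter, and then calculate a high chance of some spurious imbalance across the long variable list. The documents give neither a threshold nor a link from check to model. Many listed items (anaesthesia medication, tourniquet time, pill counts, physical therapy) arise after randomisation, so differences in them need not be chance. A chance imbalance at baseline is in any case not a false treatment finding.

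On size, the documents give balance as the reason for stratifying, state no prognostic strength, and call correlated cases uncommon, so the laterality factor may explain little. Conditional surgeon adjustment alone does no material harm in the simulation (2.9% to 5.3%), and always including surgeon as fixed effects adds no power.

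All of this stands and limits the point. It does not answer the open list, the undefined selection rule or the missing terms.

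**Conclusion.** The point holds as an improvement that costs nothing, not as a fatal flaw. The primary model is not fixed in advance; the two stratification factors and baseline pain are not named in it; and surgeon, a stated driver of the sample size, is left to later judgement without a criterion.

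The precision loss is conditional: about 2 to 5 points of power for an assumed strata R² of 0.05 to 0.20, and none at 0. Where it occurs it makes the unadjusted test conservative; it does not produce false positives. The false-positive risk comes from choosing among models. The 6.4% to 7.6% applies if the smallest of four p-values is reported, which the plan does not propose but does not rule out. All sizes rest on the back-solved SD and on assumed block size, stratum shares and R². No figure is offered for baseline pain, whose correlation with day-two pain the documents do not give.

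One named covariate needs care. The last dose of pain medication is measured after randomisation and may itself be affected by treatment, so adjusting for it can bias the treatment effect.

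**What to change.** In the Primary Outcome text under Data Analysis:

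- Prespecify one primary model with treatment, baseline pain and the two stratification factors (unilateral/bilateral, isolated/additional procedures), always included whatever the data show.
- State in advance whether surgeon is in that model, and replace the conditional wording in the Recruitment section. A random effect would be consistent with the sample-size reasoning; it is a reasonable choice, not the only one.
- Take the primary p-value from that model alone, and delete the reference to unspecified model-building rules.
- Report Table 1 descriptively, and state that between-group tests will not be used to choose covariates.
- Label every other adjusted model as a sensitivity analysis, including any with covariates measured after randomisation, such as the time of the last pain-medication dose.

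The cost is wording only. The strata, baseline pain and surgeon of record are already collected, and neither the randomisation nor the sample size changes.
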